### 11.2 Analysis of Secondary Endpoints

#### 11.21 Neuropsychological testing and mood scores

Analysis of variance with repeated measures will be used to compare neuropsychological and mood rating scores for the baseline, placebo, and active drug periods.

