### 5.2 Secondary Hypotheses

1. PRX-00023 will lead to improved anxiety and depression rating scores compared with placebo.
2. The degree of baseline 5HT1A receptor binding reduction in the epileptic focus will predict drug response.
3. Polymorphisms in SERT, TPNH, COMT, BDNF and GABA genes that have been associated with psychiatric disorders and epileptogenesis may be related to drug response.

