#### Mood rating scales:

Hamilton Depression Rating Scale-24 item  
Hamilton Anxiety Rating Scale  
Beck-2 Depression Self Inventory  
Columbia Suicide Severity Rating Scale

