## 10. Outcome Measures

The primary outcome measures for drug efficacy will be:

Mean difference in seizure frequency comparing the active and placebo periods.

Secondary outcome measures for efficacy will be:

Proportion of patients with  $\geq 50\%$  lower seizure rate on PRX-00023 than placebo

Hamilton Depression and Anxiety Rating scales

Performance on neuropsychological testing scales

Outcome measures for safety will include:

Columbia Suicide Severity Rating Scale

Hamilton Depression Rating Scale

Clinical examination

CBC and clinical chemistry studies

ECG

Adverse event reports

Seizure Calendars

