### 11.23 Polymorphism analysis

The presence or absence of the polymorphisms detected will be compared to 5HT1A receptor PET binding and seizure frequency outcome in an exploratory manner.

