### 11.4 Sample size and power calculation

We assume that the mean difference between drug and placebo will be a 15% lower seizure rate, (representing a 30% improvement on drug versus 15% improvement on placebo versus baseline), and that the standard deviation of difference is 22%.

Based on a paired t-test, the estimated sample size is 19 to obtain 80% power at a significance level of 0.05. In order to balance the two arms we will accrue patients until 20 completers have been obtained. We request a total of 30 subjects to take into account a possible 20% dropouts.

Paired t-test of mean difference equal to zero

	1	2	3	4
Test significance level, $\alpha$	0.050	0.050	0.050	0.050
1 or 2 sided test?	2	2	2	2
First condition mean, $\mu_1$	30.000	30.000	30.000	30.000

Second condition mean, $\mu_2$	15.000	15.000	15.000	15.000
Mean difference, $\mu_d = \mu_1 - \mu_2$	15.000	15.000	15.000	15.000
Standard deviation of differences, $\sigma_d$	22.000	23.000	20.000	25.000
Effect size, $\omega =  \mu_d  / \sigma_d$	0.682	0.652	0.750	0.600
Power ( % )	80	80	80	80
n	19	21	16	24

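### The mood and cognitive analysis in section 11.21 names no deciding scale, no active-versus-placebo contrast and no error control, so it does not test secondary hypothesis 1

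*Combined protocol and SAP*

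**What the plan says.** Section 5.2 states the first secondary hypothesis as a directional comparison with placebo: "PRX-00023 will lead to improved anxiety and depression rating scores compared with placebo". None of the hypotheses in 5.2 concerns cognition.

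Section 10 lists the Hamilton Depression and Hamilton Anxiety scales as secondary efficacy outcomes, together with "Performance on neuropsychological testing scales". It does not rank them. Section 7.581 lists seven cognitive tests: two of attention, two of memory and three of executive function. Its mood list holds both Hamilton scales, the "Beck-2 Depression Self Inventory" and the Columbia scale. Section 10 puts the Columbia scale under safety and does not mention the Beck-2.

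The whole analysis plan for these scores is one sentence in 11.21: "Analysis of variance with repeated measures will be used to compare neuropsychological and mood rating scores for the baseline, placebo, and active drug periods". It gives no level, order, correction or named contrast. Two neighbouring sections do qualify their analyses. The PET comparison in 11.22 carries a correction for repeated measures, and 11.23 compares polymorphisms with PET binding and "seizure frequency outcome in an exploratory manner".

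A significance level appears only in the seizure calculations of 11.4 and 11.41.

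**The concern.** There are two separate problems.

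The first is selection. With nine or ten unranked scales and no rule for which one decides, any significant scale could later be presented as a mood or cognitive effect. The chance that an inert drug yields at least one is well above the level of a single test.

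The second is the test itself. Secondary hypothesis 1 compares drug with placebo, but an overall test across three conditions asks whether baseline, placebo and active means are all equal. If scores improve from baseline under both treatments, through practice, placebo response or simply being in a trial, that test can be significant when the drug does nothing. The plan expects such a movement for seizures: section 11.4 assumes a 15% improvement on placebo versus baseline. For cognition, 7.581 lists alternate forms for only two of the seven tests.

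Mood benefit is part of the rationale in section 4 and a possible direct benefit in section 13, so a loosely defined mood result would carry weight.

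**Working it through.** **The plan's own figures.** Section 11.4: "Based on a paired t-test, the estimated sample size is 19 to obtain 80% power at a significance level of 0.05". The row "1 or 2 sided test" is entered as 2, and the assumption is that "the mean difference between drug and placebo will be a 15% lower seizure rate", with a standard deviation of the difference of 22%. Noncentral-t power for n = 19, with noncentrality (15/22)√19, is 80.2%, so 19 is reproduced. The other columns (21, 16, 24) and the table in 11.41 (12 per group, power 0.802) also reproduce. The plan gives no error rate for the secondary scales.

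**Number of scales.** Section 10: 2 Hamilton + 7 cognitive = 9. With Beck-2 from 7.581: 10.

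**Assumptions.** Each scale is tested active versus placebo at two-sided 0.05. This level is borrowed from the seizure calculation, because 11.21 states none. There is no true effect, and all pairs of scales share a common correlation ρ, which the documents do not give.

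**Chance of at least one significant scale.** If independent, it is 1 − 0.95^k. With k = 10 this is 1 − 0.95^10 = 40.1%; k = 9 gives 37.0%; k = 2 gives 9.75%. For correlated scales, write each test statistic as √ρ·Z + √(1−ρ)·e, take the probability that all k stay within ±1.96 given Z, average over Z, and subtract from 1.

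| Scales | ρ = 0 | ρ = 0.5 | ρ = 0.8 |
|---|---|---|---|
| 10 | 40.1% | 28.7% | 17.3% |
| 9 (section 10 only) | 37.0% | 26.9% | 16.6% |
| 2 (Hamilton scales) | 9.8% | 9.1% | 7.8% |

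Simulated paired t-tests with n = 20, ten scales and ρ = 0.5 gave 29.6%. The three-level F test gave 30.0% when all three condition means were equal.

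**False improvement only.** Counting only results in the favourable direction (upper limit 1.96, no lower limit) at ρ = 0.5 gives about 14% for ten scales (15% in the n = 20 simulation) and about 4.5% for the two Hamilton scales.

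**Three-condition test when only baseline differs.** Take n = 20 and an inert drug. Placebo and active share the same mean, shifted from baseline by d standard deviations of the paired difference. With equal variances and covariances, that standard deviation is σ√2, where σ is the within-patient residual standard deviation, so the shift is d√2·σ. The condition means deviate from their average by −2/3, +1/3 and +1/3 of the shift, and the squares sum to 2/3. The noncentrality is therefore n × 2d² × 2/3. For d = 0.5 this is 20 × 0.5 × 2/3 = 6.67. The 5% critical value of F with 2 and 38 degrees of freedom is 3.245, and the chance of exceeding it is about 60%. The same formula gives 18% at d = 0.25 and 93% at d = 0.75. The active-versus-placebo contrast stays at 5% throughout, because the shared shift cancels.

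**The case against.** The trial is called a pilot, has one primary endpoint and aims for about 20 completers. These scales are classed as secondary, and no passage says that a secondary result will support an efficacy claim. Formal error control over secondary outcomes in such a trial is partly a matter of preference. This stands, and it limits both the weight of the point and the remedy.

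Several stronger readings are tempting but not supported:

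- A reader might take 29% as the plan's false-positive rate. It needs a correlation of about 0.5, which the documents do not give, and an active-versus-placebo test that 11.21 does not define. Only the range, with its assumptions, can be stated.
- A reader might infer that every scale is tested at 0.05. Section 11.21 gives no level.
- A reader might infer that the scales are confirmatory because the polymorphism analysis is called exploratory. Labelling one analysis does not fix the status of another.
- A reader might count any significant Hamilton result as support for hypothesis 1. The hypothesis is directional, and it names anxiety and depression together. If both scales must show benefit, there is no inflation; the plan does not say.
- A reader might see a precedent in section 4.42: CP-007 missed its anxiety endpoint (p = 0.116) while a depression score was significant, and CP-020 found no significant difference on that score. The two trials differed in population and dose, and CP-020 is not described as a test of the CP-007 result. The parallel is a caution at most.

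The pilot label does not answer the mismatch between a hypothesis against placebo and an overall test that includes baseline.

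**Conclusion.** The point holds as a gap in specification that should be closed. The one-sentence analysis leaves open which scale decides hypothesis 1 and which comparison is made, and its three-condition test does not address a hypothesis stated against placebo.

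The multiplicity is material for the full set of scales and modest for the two Hamilton scales, on the assumed level and correlations tabulated above. The baseline problem depends on a shift the documents do not quantify for these scales, so its 60% illustrates the mechanism rather than predicts this trial. The primary seizure comparison keeps its error rate.

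A reader might conclude that the mood tests must be gated on the seizure result, or that the 50% responder outcome must be made exploratory. The documents do not call for either. Mood is a separate stated hypothesis, and gating would block it in about one trial in five even under the planned seizure effect (1 − 0.80). The responder outcome is not covered by 11.21.

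**What to change.** Before unblinding, amend 11.21 as follows.

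1. Test secondary hypothesis 1 by the within-patient active-versus-placebo contrast on Hamilton Depression (24-item) and on Hamilton Anxiety, each at the end-of-MTD visit, and state the two-sided level.
2. Choose one rule and write it down. Either both contrasts must be significant in favour of the drug, each at 0.05, or a Holm correction applies across the two, with the smaller p-value tested at 0.05/2 = 0.025 and the other at 0.05 if the first succeeds. Either rule holds the error for the Hamilton claims to at most 5%.
3. Report the Beck-2, all cognitive scores and the 6-week Hamilton Depression score as exploratory active-versus-placebo estimates with 95% confidence intervals and no efficacy claim.

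This costs a few sentences and no patients, visits or data. The price is that the cognitive scales and the Beck-2 can no longer carry a claim on their own, and the Hamilton claim becomes slightly stricter.

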#### 7.52 Randomization to Active drug or Placebo

Subjects will be randomized at the end of baseline to either active drug or placebo using a 1:1 ratio per the randomization schedule. The randomization schedule will be generated, secured, distributed, and stored by the NIH Pharmacy. Patients may be outpatients or inpatients during titration depending on their geographical location, need for additional education on the titration process or if they are participating in concurrent studies with the Clinical Epilepsy Section. All patients will be given an exact written titration schedule to follow.

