#### 7.53 Period 1:

During Period 1 there will be regular communication with patients/families by phone, secure email, and/or the clinical trial database. Communication with patients/families will occur approximately 6 times during each treatment period, about once every two weeks.

PRX-00023 or matching placebo will be titrated up starting at an oral dose of 40 milligrams (Mg) twice daily for five days; the dose will then be increased to 80 milligrams twice daily for five days, and then to 120 milligrams twice daily for approximately 70 days. After which the dose will be tapered off as follows: 80 milligrams twice daily for five days, 40 milligrams twice daily for five days, followed by discontinuation of study drug. If patients experience side effects during the titration up, the next scheduled dose increase will be delayed until they abate. If this does not occur, the dose will be reduced in 40mg per day increments. Period 1 will last approximately 12-16 weeks. The above description and table below provides a targeted dosing schedule, however, adjustments may be made if, for example, the patient experiences side effects during titration.

	Titration		MTD	Taper	
Day	Day 0-4	Day 5-9	Day 10-79	Day 80-84	Day 85-90
No. of days	5 days	5 days	70 days	5 days	5 days
Dose	40mg bid	80mg bid	120mg bid	80mg bid	40 mg bid

Patients will keep seizure calendars. Patients will return to NIH 6 weeks +/- 2 weeks after the start of Period 1 and the tests listed in section 7.571 will be performed. At the end of the Maximum Tolerated Dose (MTD) period, patients will again return to NIH for repeat of baseline testing (see section 7.572). Following testing, patients will be tapered off of Period 1 study drug and begin washout period.

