#### Memory:

Hopkins Verbal Learning Test, versions 1,3 &4 (Brandt and Benedict 2001).  
Brief Visuospatial Memory Test-Revised (Benedict 1997)

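### Section 11.21 compares baseline, placebo and active together and names no active-versus-placebo contrast, so the overall test can be significant when the drug does nothing

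*Combined protocol and SAP*

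**What the plan says.** Section 11.21 is a single sentence, which plans a repeated-measures analysis of variance "to compare neuropsychological and mood rating scores for the baseline, placebo, and active drug periods". It gives no contrast, follow-up comparison, decision rule or list of model terms.

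The hypothesis that the mood scores serve is in section 5.2: "PRX-00023 will lead to improved anxiety and depression rating scores compared with placebo". Section 10 lists the "Hamilton Depression and Anxiety Rating scales" and the neuropsychological scales as secondary efficacy outcomes.

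On timing, section 7.52 states that "Subjects will be randomized at the end of baseline to either active drug or placebo using a 1:1 ratio", and section 7.53 that at the end of the MTD phase "patients will again return to NIH for repeat of baseline testing". Section 7.55 repeats this for Period 2. Each patient is therefore tested first at baseline and then at the end of each treatment period, and only the order of active and placebo is randomised.

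Section 7.581 gives alternate forms for two cognitive tests: "Hopkins Verbal Learning Test, versions 1,3 &4" and three forms of the Controlled Oral Word Association Test. It states none for the others.

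For seizure frequency, section 11.1 does specify a paired active-versus-placebo test and a check for an order effect. Nothing equivalent is written for mood or cognition.

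**The concern.** The null hypothesis of a three-level test is that baseline, placebo and active all have the same mean. The null that belongs to secondary hypothesis 1 is only that active equals placebo. The two differ whenever patients change by the same amount in both treatment periods, because the first null is then false while the second is true.

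The plan itself expects shared change. Section 11.4 assumes a 15% seizure improvement on placebo, and section 12.5 says that placebo effects are seen in every trial of antiepileptic drugs. Section 4.42 reports that HAM-A fell on placebo in the earlier anxiety trial. The cognitive tests are given three times.

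If the overall F test is the result that is reported, a significant finding for mood or cognition could be read as support for the drug when the drug had no effect.

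**Working it through.** **The plan's own figures.** The documents give no sample size or power for the mood and cognition analysis. The only paired calculation is for seizures in section 11.4: difference 15, SD of differences 22, two-sided 0.05. The noncentral t distribution gives power 0.802 at n = 19, so the stated 19 reproduces. It is not in dispute and is unaffected by this point.

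**Inputs.**
- n = 20, from section 11.4 ("we will accrue patients until 20 completers have been obtained"); n = 24 from section 11.41 as a variant.
- Two-sided alpha 0.05.
- Shared shift δ from baseline, in SD units: assumed 0.1 to 0.5.
- Within-patient correlation ρ: assumed 0.5 to 0.7, with 0.3 as a check.
- Normal scores with equal variances and equal correlations.

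**Formula.** With no drug effect the three means are 0, δ and δ. Their mean is 2δ/3, and the sum of squared deviations is 4δ²/9 + δ²/9 + δ²/9 = 2δ²/3. The overall F test has 2 and 2(n − 1) degrees of freedom and noncentrality

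λ = n × (2δ²/3) / (1 − ρ).

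**Worked example.** For n = 20, δ = 0.5 and ρ = 0.5: λ = 20 × 0.1667 / 0.5 = 6.67. The critical value of F(2, 38) is 3.245, and the probability of exceeding it is 0.596.

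**Probability that the overall test is significant when active equals placebo, n = 20:**

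| Shared shift (SD) | ρ = 0.3 | ρ = 0.5 | ρ = 0.6 | ρ = 0.7 |
|---|---|---|---|---|
| 0.1 | 6% | 7% | 7% | 8% |
| 0.2 | 11% | 13% | 15% | 19% |
| 0.3 | 19% | 25% | 30% | 39% |
| 0.5 | 45% | 60% | 70% | 83% |

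At n = 24 and a 0.5 SD shift, the range for ρ from 0.5 to 0.7 is 69% to 90%.

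**Cross-check by simulation** (20,000 trials per setting, balanced sequences, n = 20, ρ = 0.5).
- Shared shift 0.3 SD: overall test 25.1%, active-minus-placebo contrast 4.9%.
- Shared shift 0.5 SD: overall test 59.9%, contrast 4.9%. In 55% of these trials the overall test is significant and the contrast is not.
- Practice gain of 0.3 SD at the second testing and 0.6 SD at the third: overall test 48.4%, contrast 3.9%.
- No shift: overall test 4.6%, contrast 5.0%.

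**Role of a period term.** With n = 20, ρ = 0.7 and a 0.5 SD gain from the first to the second treatment period, a paired contrast without period rejects in 2% of null trials and has 65% power for a 0.5 SD drug effect. With period in the model these become 5% and 78%.

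**The case against.** The strongest reply is that section 11.21 is brief rather than wrong. It does not call the test an overall one and gives no decision rule, and a repeated-measures model with an active-versus-placebo contrast would fit its wording. A reader might infer that the plan excludes that contrast. The text does not support this: the contrast is unspecified, not forbidden. What remains is that the three-level comparison is the only one written down, and that choosing the contrast later, across several scores, is what a plan should prevent.

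A second reply is that the rejection rates depend on assumed shifts and correlations. That is so. At 0.1 SD the excess over 5% is small. The direction does not depend on the assumptions: any shared shift raises the rate above 5%.

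A third is that practice is partly handled. The alternate forms for the verbal learning and word-fluency tests reduce it, and practice has little bearing on mood scales. This limits the practice argument to the other cognitive tests and leaves placebo response as the route for mood. The support there is indirect, because the HAM-A fall on placebo came from patients with generalised anxiety disorder and section 4.42 gives no baseline value for it.

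**Conclusion.** The point holds. As written, section 11.21 does not commit to the comparison that secondary hypothesis 1 states, and a significant three-level result would not by itself support that hypothesis. Under the assumptions above, the rate of significant results without a drug effect runs from about 7% to 83%, against about 5% for the direct contrast. These endpoints are secondary, and the primary seizure analysis is untouched.

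Three stronger readings are tempting and should not be drawn.
- *The three-level test loses power for a real drug effect.* This is not generally true. At n = 20, ρ = 0.5 and a 0.5 SD drug effect, with placebo equal to baseline, the overall test has 59.6% power and the contrast 56.5%. The overall test falls behind, at 47%, when baseline lies midway between the two treatments.
- *Selection at entry makes mood scores regress to the mean.* Section 6.2 selects on seizure count, and neither 6.2 nor 6.3 requires a minimum depression or anxiety score, so the documents give no direct basis for this.
- *Leaving out a period term inflates false positives.* With balanced sequences it does not. The active-minus-placebo contrast becomes conservative and less powerful.

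**What to change.** Reword section 11.21 so that the test for each mood and neuropsychological score is the within-patient active-minus-placebo contrast at the end of the MTD phase. Estimate it from a mixed model with treatment and period as fixed effects (and sequence, if wanted) and patient as a random effect. State that the period term is there for precision. Report change from baseline descriptively. Because the Hamilton depression scale is also taken at the six-week visit (section 7.571), say that the end-of-MTD value is the one tested.

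This needs no new data, visits or patients and leaves the sample size unchanged. The small cost is that the baseline comparison named in 11.21 becomes descriptive.

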### 11.22 5HT1A Receptor Binding

FCWAY functional images will be corrected for partial volume effects as previously described, and gray-white matter ratios on a pixel by pixel basis. Regions of interest drawn on MRI scans will be co-registered with the PVC-corrected V images. For each patient, side-side asymmetry values will be obtained, in order to detect alterations of binding ipsilateral to the epileptic focus.

A binding potential measurement will be derived using the cerebellum as a region devoid of 5-HT1A receptors, and calculated as:

$$BP = [(V_{ROI} - V_{CEREB}) / f_1] \quad (\text{Eq. 1})$$

where  $V_{ROI}$  and  $V_{CEREB}$  are the distribution volumes in the target ROI and in the cerebellum respectively, and  $f_1$  is [F]FCWAY plasma free fraction.

Values in regions of interest will be compared between baseline and peak dose scans using a paired Student's T-test with correction for repeated measures. It is anticipated that 12 subjects will have a scan at baseline and on active drug, while 12 will have a scan at baseline and on placebo, providing a measure of test-rest reliability.

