Objective: To initiate a pilot clinical trial assessing the safety, tolerability and efficacy of the 5HT1A receptor agonist PRX-00023 in patients with localization-related epilepsy. PRX-00023 is a 5HT1A receptor agonist that has shown promise in clinical trials of depression (Rickels et al 2008). Patients with localization-related epilepsy have reduced 5HT1A receptor binding on 18FCWAY positron emission tomography (PET). (Toczek et al 2003) Increasing neurotransmitter activity at 5HT1A receptor sites might ameliorate seizures. Moreover, depression is a common co-morbidity in people with epilepsy (Theodore et al 2006). Altered 5HT1A receptor binding has been found in depression.

Study Population: Thirty adults with localization-related epilepsy.

Design: A randomised, double blind, placebo-controlled cross-over, phase II clinical trial. Subjects will be screened under protocol 01-N-0139 and will undergo medical and epilepsy history and physical examination, vital signs, ECG, clinical laboratory studies including standard clinical chemistry and hematology studies, urinalysis, pregnancy test for females of childbearing potential, and MRI scan and video EEG monitoring will be performed if not previously completed successfully, and measurement of plasma AED levels (for those AEDs in which an assay is available at NIH).

The trial will have a baseline phase, which will last up to 6 weeks. Baseline may occur concurrent with screening procedures. The baseline phase will include measurement of seizure frequency (patient will record via seizure calendar). In addition the following will be administered, unless previously completed: Columbia Suicide Severity Rating Scale, neuropsychological and mood evaluations, FCWAY PET (if not already performed), EEG, measurement of plasma AED levels (if assay available), and pregnancy test (for women of child bearing potential), saliva samples will be obtained for genetic testing (if not previously obtained) and blood samples will be obtained during the PET procedure for cortisol and ACTH levels.

Following baseline, patients will begin the treatment phase (consisting of Period 1 and Period 2). Patients will be randomized to PRX-00023 (120mg BID) or matching placebo. After completion of the first treatment period, patients will undergo a washout period after which patients will be crossed over to the alternate treatment period.

Outcome measures:

1. Seizure frequency counts during the 3 month placebo and active treatment phases

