### 7.51 Baseline:

Baseline phase may occur concurrent with screening procedures and may last up to 6 weeks. During baseline, patients will record seizures on a seizure calendar, while on their baseline treatment with one or two AEDs. They will be eligible for this study if they have at least four seizures during a 6-week baseline phase. If patients have 4 seizures in less than six weeks, they do not need to wait the entire 6-weeks to begin Period 1 of the treatment phase. No changes in

patients' baseline AEDs will be allowed during this period, or subsequent study phases. Patients who use sublingual lorazepam for seizure clusters may continue to do so.

During the Baseline phase the following tests (described in section 7.57 and 7.58) will be performed (unless previously completed, as noted):

Columbia Suicide Severity Rating Scale

Neuropsychological testing

Mood testing

Measurement of plasma AED levels, if assay available

Pregnancy test

EEG

18F-FCWAY PET to measure 5HT1A receptor binding (if not already performed)

Saliva samples to test for polymorphisms in SERT, TPNH, COMT, BDNF and GABA genes that have been associated with psychiatric disorders and epileptogenesis (if not previously performed)

Blood samples for cortisol and ACTH level will be obtained at the time of PET (if performed).

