### 7.582 PET Scan:

A PET scan with 18F-FCWAY and a transmission scan will be performed once (if patients have not had them already) in a single session before initiation of study drug.

For the PET scans, patients will be in a fasting state for three hours prior to the procedure. Patients may not use any alcohol or recreational drugs for the two weeks preceding the PET scan. EEG leads may be attached to the scalp to record EEG during the PET scan if warranted by the patient's seizure pattern. The thermoplastic facemask will be used in the standard manner for NIH PET scans. An IV infusion of 0.9% saline solution will be started to provide IV access for radiotracer administration.

Following transmission scans, 10 mCi of [F-18]FCWAY will be administered. Scanning will proceed for 120 minutes. If necessary, scanning can be interrupted to allow the patient to sit up and rest, and resumed for the remainder of the predetermined time.

During the [F-18]FCWAY study, up to 40 arterial blood samples (approximately 250 cc) will be collected and radioactivity concentration in whole blood and plasma will be determined. A catheter will be placed in the patient's radial artery by the NIH Anesthesia Department. The skin at the site of the puncture will be anesthetized with 1% lidocaine. The catheter will be perfused (3ml/hr) with heparin solution (600 units/l) during the procedure. The amount of heparin infused will be much smaller than the amount necessary to produce any systemic anticoagulant effect. The arterial input function is necessary for quantitation of 5HT1A receptor volume of distribution. In addition, at selected sample times, samples will be used to measure the fraction of the radioactivity in plasma that has not been metabolized. The fraction of plasma radioactivity unbound to protein will also be determined.

Scans will be performed with the PET/CT or the High Resolution Research Tomograph (HRRT). The slice separation is 2.0 mm. The transverse resolution is 4.4 mm in HIREZ and the axial resolution is 4.5 mm in HIREZ. All scans will be acquired in 3D mode and start with an 8-min transmission scan with 2 rotating rod sources for the purpose of attenuation correction.

Blood samples for cortisol and ACTH level will be obtained at the time of PET, through the A line or IV line.

IV and arterial catheters will be removed after scanning is completed. The patient will be asked to urinate after the scan and again two hours later.

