7.583 Genetic Testing:

Testing for polymorphisms in genes related to serotonin transport, depression, and epileptogenesis

If patients have not provided DNA samples previously, we will obtain saliva samples to test for polymorphisms in SERT, TPNH, COMT, BDNF and GABA genes that have been associated with psychiatric disorders and epileptogenesis. DNA testing is optional.

Samples and data may be used for comparison with samples from epilepsy patients and normal controls obtained in future studies.

DNA and cell lines will be processed, tested for polymorphisms, and maintained in the Laboratory of [name], NIAAA, using the established procedures of his laboratory.

7.584 Total blood to be drawn

Screen	Baseline	Treatment Phase Period 1 6 Weeks (+/- 2 weeks) and 12 -16 Weeks	Wash out 4-6 weeks	Treatment Phase Period 2 6-weeks (+/- 2 weeks) and 12-16 Weeks	Approx. 1 month post study follow up
Acute care panel and Hepatic panel 10 mL	AED level 8 – 16 mL	Acute care panel and Hepatic panel 30 mL		Acute care panel and Hepatic panel 30 mL	Acute care panel and Hepatic panel 8 mL
CBC 3 mL	ACTH 2 mL Done with PET	CBC 9 mL		CBC 9 mL	CBC 3 mL
AED level 8 – 16 mL	Cortisol 10 mL Done with PET	AED level 24 - 48 mL		AED level 24 – 48 mL	AED level 8 – 16 mL

	PET study 250 mL				
Max 29 mL	Max 278 mL	Max 87 mL		Max 87 mL	Max 29 mL

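### The PET analysis in 11.22 needs on-treatment scans that no section in hand schedules, and secondary hypothesis 2 has no test assigned to it.

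*Combined protocol and SAP*

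**What the plan says.** **The planned PET analysis.** Section 11.22 states: "Values in regions of interest will be compared between baseline and peak dose scans". The test is a paired t-test with an unnamed correction for repeated measures. On numbers it says: "It is anticipated that 12 subjects will have a scan at baseline and on active drug"; another 12 are expected to have a baseline scan and one on placebo, to give test-retest reliability.

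**The scheduled scans.** Section 7.582 says a PET and transmission scan "will be performed once (if patients have not had them already) in a single session before initiation of study drug". The precis and section 7.51 also place PET at baseline, for patients who have not had it. The 6-week list (7.571), the end-of-MTD list (7.572) and the final visit (7.56) do not include it. In the blood table (7.584) the entry "PET study 250 mL" stands in the baseline column only.

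**The binding hypothesis.** Secondary hypothesis 2 (5.2) is that the degree of baseline binding reduction in the epileptic focus predicts drug response. Section 11.22 defines two measures. One is asymmetry: "side-side asymmetry values will be obtained, in order to detect alterations of binding ipsilateral to the epileptic focus". The other is the binding potential (BP) of Eq. 1. Section 10 lists two seizure outcomes: the active-placebo difference in frequency, and the proportion of patients with a seizure rate at least 50% lower on drug than on placebo. Section 11.23 compares polymorphisms with binding and with seizure outcome.

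**The concern.** There are two linked problems. First, the only PET test written down compares a baseline scan with a scan under treatment, and the procedures supply only the first of these. Second, the hypothesis that could be tested with the single baseline scan has no analysis. Section 11.22 is about change in binding; 11.23 is about genotype; neither relates baseline binding to response.

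If this is left alone, the PET section cannot be carried out as written. With two binding measures and two seizure outcomes open, whoever analyses hypothesis 2 would have four combinations to choose from, possibly after unblinding. If all four were tested at 0.05, the chance of at least one false positive would be 1 - 0.95^4 = 0.185, treating them as independent for illustration.

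**Working it through.** **1. Does the blood table leave room for a second scan?** This is the only numeric schedule that shows when PET is done (7.584, maximum volumes).
- Baseline: AED level 16 + ACTH 2 + cortisol 10 + PET 250 = 278 mL, as printed.
- Each treatment period: panels 30 + CBC 9 + AED level 48 = 87 mL, as printed.
- A treatment period with a scan would be 87 + 250 = 337 mL, or 349 mL with ACTH and cortisol. Neither total appears.

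**2. Pairs available.** Expected in 11.22: 12 + 12 = 24. Scheduled in 7.51, 7.56, 7.571, 7.572, 7.582 and 7.584: 0.

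**3. Do other phrases add a scan?** Section 7.53 has patients return at the end of the MTD period to repeat the baseline tests, but it defines those by reference to 7.572, which has no PET. The plural in references to PET scans (7.5, 7.582, 14) is generic and schedules no session.

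**4. What can the single scan support for hypothesis 2?** Take a regression of the within-patient seizure contrast on baseline asymmetry, with treatment sequence as one covariate. Inputs are n = 20 or 24 completers (6.1), two-sided 0.05, 80% power, and the 22-point SD of the difference (11.4). That SD belongs to the section's paired t-test, whose n of 19 is reproduced by exact noncentral-t power (0.802).

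Detectable partial correlation (Fisher z): tanh[(1.960 + 0.842)/sqrt(n - 4)]
- n = 20: tanh(2.802/4.000) = 0.605
- n = 24: tanh(2.802/4.472) = 0.556

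95% CI half-width per SD of asymmetry: t(0.975, n - 3) × SD/sqrt(n - 1), ignoring chance imbalance of asymmetry between sequences.

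| SD of contrast | n = 20 | n = 24 |
|---|---|---|
| 22 (section 11.4) | 2.110 × 22/4.359 = 10.6 | 2.080 × 22/4.796 = 9.5 |
| 35 (simulated, low) | 16.9 | 15.2 |
| 52 (simulated, high) | 25.2 | 22.5 |

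**5. Why the 22-point SD may be optimistic.** The contrast was simulated with Poisson counts over 12 weeks per period. The assumptions, which the documents do not supply, were log-normal seizure rates (median 8 per 6 weeks, log SD 0.8) and an SD of the patient log treatment ratio of 0.3 to 0.5. At least 4 baseline seizures and a 30% versus 15% reduction follow 6.2 and 11.4. Baseline either ran the full 6 weeks or ended at the fourth seizure. On the percent-of-baseline scale the SD of the contrast was about 35 to 52 points. The false-positive rate was about 5%. Power at a true correlation of 0.4 between asymmetry and the log treatment ratio was about 15 to 29% over both sample sizes.

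**The case against.** The strongest reply is that part of the gap closes on a fair reading, and some of it does.

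- **A response definition exists.** A reader might infer that the plan never defines drug response. Section 10 gives two usable seizure outcomes, one of them a 50% responder measure. What is missing is the assignment of either to hypothesis 2.
- **Asymmetry is the natural measure.** Its stated purpose in 11.22 comes close to the wording of hypothesis 2. That is a good reason to choose it, but the plan does not do so.
- **24 against 20.** A reader might infer that 12 + 12 rescanned patients contradict the goal of 20 completers. The documents do not support that. Section 6.1 provides for 24 completers if carry-over is found, 11.5 seeks 24 subjects with up to 30 enrolled, and a rescan in Period 1 would not need crossover completers.
- **Unseen attachments.** The Study Calendar and Form NIH 88-23a (radiation) were not available and might list a second scan. If they did, they would contradict 7.582, so reconciliation would still be needed.
- **Importance.** This is a pilot trial and section 10 lists no PET outcome. That limits the consequences. Selection after unblinding is a possibility that the text leaves open, not something that it shows.

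The contradiction between 11.22 and 7.582, and the absence of a test for hypothesis 2, stand.

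**Conclusion.** The point holds and should be fixed. On the sections available, the test in 11.22 has 0 of its 24 expected pairs, so neither the paired comparison nor the reliability estimate can be computed. Hypothesis 2 has candidate measures and outcomes but no assigned combination and no test.

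The documents do not show which side of the contradiction is intended. Nor do they support extending the point to the primary seizure analysis or its sample size, neither of which uses PET.

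A replacement analysis on the single scan is feasible but imprecise. The half-width is about 10 points per SD of asymmetry if the 22-point SD of 11.4 carries over, and about 15 to 25 points under the simulated count model. The second range rests on assumed seizure rates. On either basis only a strong relation would be detected.

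**What to change.** Reconcile 11.22 with 7.582, 7.572 and 7.584.

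**If on-treatment scans are intended,** those sections must list them, and the blood totals must change.

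**If the single scan stands,** delete the final paragraph of 11.22 and replace it with one exploratory analysis, fixed before unblinding:
- Response: the within-patient placebo-minus-active seizure contrast, as percent of baseline (the scale of 11.4).
- Predictor: baseline side-side asymmetry of Eq. 1 BP in the region of the epileptic focus, as localised before randomisation. Write out the asymmetry formula.
- Model: linear regression with treatment sequence included, to allow for period. Report the slope with a 95% CI.
- If carry-over is detected and the paired contrast is dropped under 11.1: use the Period 1 change from baseline with treatment, asymmetry and their interaction.

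The cost is protocol and SAP wording, with no added scans or patients. The price is low precision: the result must be labelled exploratory, and a null finding cannot exclude a moderate relation. Patients without a lateralised focus have no asymmetry value and drop out, which lowers n further.
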